**Table 3: Dose Escalation and De-Escalation Algorithm for the “rolling 6” Design**

Subjects Enrolled a	Number of Subjects and DLT Status		Next Enrollment Dose Level ( $\text{g/m}^2$ per day)		
	Subjects with DLT	Subjects without DLT b	Current Dose level $1.0 \text{ g/m}^2$ per day	Current Dose level $2.0 \text{ g/m}^2$ per day	Current Dose level $1.5 \text{ g/m}^2$ per day
2	0,1 2	0,1,2 0	1.0 Stop c	2.0 1.5	1.5 MTD=1.0
3	0,1 0 ≥2	0,1,2 3 Any	1.0 2.0 Stop c	2.0 2.0 1.5	1.5 1.5 MTD=1.0
4	0,1 0 ≥2	0,1,2,3 4 Any	1.0 2.0 Stop c	2.0 2.0 1.5	1.5 1.5 MTD=1.0
5	0,1 0 ≥2	0,1,2,3,4 5 Any	1.0 2.0 Stop c	2.0 MTD 1.5	1.5 MTD MTD=1.0
6	0,1 0,1 ≥2	0,1,2,3,4 5,6 Any	Suspend 2.0 Stop c	Suspend MTD 1.5	Suspend MTD MTD=1.0

Note: This algorithm selects  $1.0 \text{ g/m}^2$  as the MTD and stops the entire enrollment once  $1.5 \text{ g/m}^2$  exceeds the MTD. Total number of evaluable subjects at dose level  $1.0 \text{ g/m}^2$  can be as few as 3.

a Subjects complete Cycle 1 and evaluable for DLT, or with pending data, excluding non-evaluable subjects.

b Subjects complete Cycle 1 and evaluable for DLT.

c Dose level  $1.0 \text{ g/m}^2$  exceeds MTD.

Up to 18 evaluable subjects may be enrolled if the intermediate cytarabine dose level ( $1.5 \text{ g/m}^2$  per day) is tested and all 3 dose levels recruit 6 subjects.

Subjects enrolled in the Phase 2 portion of the study will receive sequential administration of DACOGEN and cytarabine with the MTD of cytarabine, determined in Phase 1.

For subjects enrolled in either the Phase 1 or Phase 2 portion of the study, treatment may be repeated for up to 4 cycles with the sequential administration of DACOGEN followed by cytarabine. Subjects in Phase 1 can receive up to 4 cycles at their current dose level of cytarabine if an MTD for cytarabine has not been established. Once an MTD for cytarabine is declared, subjects who are receiving cytarabine at a dose other than the MTD for less than 4 cycles can receive the MTD dose of cytarabine for their remaining cycles as long as only 4 cycles total are administered. Subjects may continue to be treated with DACOGEN as monotherapy ( $20 \text{ mg/m}^2$  IV infusion over 1 hour for 5 consecutive days every 28 days) in the Continuation Phase as long as they are considered to derive benefit in the investigator's opinion. During this period subjects will be assessed for safety, concomitant therapies, and adverse events and disease assessment as clinically indicated.

### 6.3.1. Dose Delays

Cycles may be delayed up to 28 days to allow for recovery from toxicity. Subjects with bone marrow aplasia/hypoplasia (defined as overall marrow cellularity less than 25%) or absolute neutrophil count (ANC)  $<0.5 \times 10^9/L$  or non-transfusion dependent platelet count  $<25 \times 10^9/L$  should not start their next cycle until further hematopoietic recovery. The DACOGEN dose will be held constant but the cytarabine dose may be adjusted for toxicity.

## 7. TREATMENT COMPLIANCE

Study drugs will be administered as IV infusions by qualified study-site personnel and the details of each administration will be recorded in the electronic Case Report Form (eCRF; (including date, start and stop times of the IV infusion, and volume infused). Under these conditions treatment compliance is ensured.

## 8. PRESTUDY AND CONCOMITANT THERAPY

All prior therapies for AML must be recorded. CNS-directed intrathecal therapy administered within 30 days before the first dose of study drugs must be recorded.

Prophylactic intrathecal therapy and hydroxyurea are allowed until 1 day prior to Cycle 1 Day 1.

Concomitant therapies must be recorded throughout the study beginning with start of the first dose of study drug to 30 days after the last dose of study drug.

Concomitant therapies allowed under this protocol are:

- Packed red blood cell transfusion: transfusions may be given as clinically indicated
- Platelet transfusion: to be administered when platelets are  $<10,000/\mu L$  or according to institutional standards.
- Prophylactic antibiotics will be administered according to institutional standards.
- Management of febrile neutropenia should be in accordance with institutional standard:

Febrile neutropenia is defined as a body temperature of at least:

38.5°C on 1 occasion or 38°C on 2 occasions when the ANC is  $<1000/\mu L$ . Febrile patients are to be evaluated by physical exam, complete blood count (CBC) with differential, and blood culture. Patients with febrile neutropenia or suspected sepsis on the basis of physical exam are to be hospitalized for appropriate broad-spectrum antibiotic coverage, consistent with local pathogen sensitivities.

- Anti-emetics and other agents needed for supportive care may be given in accordance with institutional treatment standards
- Any other medications required for clinical management of the patient
- Other than the study agents, patients cannot receive other anticancer chemotherapy during this study.

The sponsor must be notified in advance (or as soon as possible thereafter) of any instances in which prohibited therapies (eg, other anticancer medications) are administered.

## 9. STUDY EVALUATIONS

### 9.1. Study Procedures

#### 9.1.1. Overview

The Time and Events Schedule summarizes the frequency and timing of the assessments applicable for this study before and during the Sequential Treatment period, the Continuation Phase for subjects electing to receive DACOGEN single-agent therapy, and the Follow-up period after the end of any study treatments.

All subjects will be followed from the first day of sequential therapy (Day 1 of Cycle 1) according to the assessment schedule outlined in the Time and Events Schedule regardless of whether the patient completes or discontinues sequential therapy (DACOGEN followed by cytarabine). Study assessments will be performed only after written informed consent/assent is obtained. Every effort should be made to keep subjects on the study schedule as planned from Study Day 1. At each visit, study assessments should be completed before the administration of the study drugs. Every effort should be made to conduct disease evaluations as per schedule; however, post-baseline disease evaluations may be conducted  $\pm 3$  days from the scheduled visit date (based on Study Day 1), if necessary. At the following visit, the subject should return to the original planned schedule. Any missed visits, tests not performed, or examinations that are not conducted must be reported as such on the electronic case report form (eCRF).

Sample collections for biomarker and pharmacokinetic assessments should be kept as close to the specified times as possible. Other measurements may be done earlier than specified, if needed. Actual dates and times of the assessments must be recorded at minimum on the laboratory requisition forms. If required, serum or urine pregnancy tests may be performed, as determined necessary by the investigator or required by local regulation, to establish the absence of pregnancy at any time during the subject's participation in the study.

The total blood volume for the study is approximately 69 mL: 2 ml for cytogenetic assessment, 50 mL for safety and efficacy (including peripheral blood counts), 3.5 mL for PK, 6 mL for pharmacodynamic assessments, and 7.5 mL for biomarkers ([Table 4](#)).

**Table 4: Volume of Blood to be Collected From Each Subject**

Type of Sample a,b	Volume per Sample (mL)	No. of Samples per Subject	Total Volume of Blood (mL) c
Safety (including screening and post treatment assessments)			
- Hematology	2mL	18	36mL
- Serum chemistry d	2mL	7	14mL
Efficacy			
Pharmacokinetic samples	0.5mL	7	3.5mL
Pharmacodynamic (DNA methylation/ gene expression)	2mL	3	6mL
Biomarkers	2.5mL	3	7.5mL
Cytogenetics	2mL	1	2mL
Approximate Total			69mL

a Repeat or unscheduled samples may be taken for safety reasons or technical issues with the samples.

b Sample volumes will be adjusted according to standards for pediatric subjects

c Calculated as number of samples multiplied by amount of blood per sample.

d Serum chemistry includes serum  $\beta$ -hCG pregnancy test if urine pregnancy test is not performed at the site.

Note: An indwelling intravenous cannula may be used for blood sample collection. If a mandrin (obturator) is used, blood loss due to discard is not expected.

### 9.1.2. Screening Phase

The signed ICF/assent must be obtained before any study-specific procedures are performed. The Screening Phase begins when the first study-specific screening assessment is conducted. During the Screening Phase, eligibility criteria will be reviewed and a complete clinical evaluation will be performed. Screening procedures will be performed up to 14 days before Cycle 1 Day 1; however, results of tests such as radiologic tests, bone marrow collection for morphology, cytogenetics, and either immunohistochemistry or immunofluorescence performed up to 28 days before Cycle 1 Day 1 as routine work-up for the subject's disease can be used. Cardiac function must be normal, defined as shortening fraction of  $\geq 29\%$  by echocardiogram or LVEF  $> 58\%$ . Results obtained prior the screening period are acceptable provided no potentially cardiotoxic therapy was provided between that evaluation and the first dose of decitabine (Cycle 1 day 1). A negative pregnancy test for females of childbearing potential must be documented within 7 days before the Cycle 1 Day 1 dosing. If a pregnancy test result is more than 7 days old at Cycle 1 Day 1, then the test must be repeated locally and documented.

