#### **4. SUBJECT POPULATION**

This is a Phase 1-2 pediatric study of a sequential combination of DACOGEN plus cytarabine in children with relapsed or refractory AML 1 month of age to less than 18 years old. Screening for eligible subjects will be performed within 14 days before administration of any study drug.

The inclusion and exclusion criteria for enrolling subjects in this study are described in the following 2 subsections. If there is a question about the inclusion or exclusion criteria below, the investigator should consult with the appropriate sponsor representative before enrolling a subject in the study.

For a discussion of the statistical considerations of subject selection, refer to Section 11.2, Sample Size Determination.

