##### **4.1. Inclusion Criteria**

Each potential subject must satisfy all of the following criteria to be enrolled in the study.

1. Subject must be 1 month of age to <18 years of age at the screening visit.
2. Subject must have a histological diagnosis of AML according to the WHO classification
3. Criterion modified per Amendment INT-1:
  - 3.1. Subject must have AML which has relapsed or is refractory to standard of care and no curative therapy exists
    - Subjects in relapse must have at least 5% blasts in the bone marrow, with or without extramedullary disease and immunophenotypic confirmation of AML. Subjects who relapsed post- bone marrow transplant (BMT) are allowed, provided >3 months has elapsed since BMT and the subject does not have active graft-versus-host disease.
    - Subjects refractory to previous chemotherapy must have at least 20% blasts in the bone marrow
4. Subject must have a Karnofsky or Lansky score of at least 50
5. Subject must be recovered from acute toxicity of any prior treatment

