## 6. Inclusion criterion has been modified:

6.1 Criterion modified per Amendment INT-1

6.2 Criterion modified per Amendment INT-2

Subject must have adequate organ function, defined as:

- Normal renal function defined as a creatinine clearance of at least 90 mL/min/1.73 m^2 as determined using the Schwartz equation. Glomerular Filtration Rate (ml/min/1.73 m^2) = k\*Height(cm)/serum creatinine (mg/dL) where k is a proportionality constant which varies with age and is a function of urinary creatinine excretion per unit of body size; k is 0.45 for children up to 12 months of age, 0.55 for older children and adolescent girls and 0.70 for adolescent boys (adolescent is referring to 12 to 18 years of age).
- Alanine aminotransferase (ALT)  $\leq 5 \times$  upper limit of normal (ULN) and total bilirubin less than  $1.5 \times$  ULN. If ALT is transiently elevated and clearly related to recent prophylactic intrathecal treatment since start of screening but prior to the first dose of decitabine, it should be discussed with the sponsor's medical monitor whether the dose can be started or should be postponed.
- Cardiac function must be normal, defined as shortening fraction of  $\geq 29\%$  by echocardiogram, or left ventricular ejection fraction (LVEF)  $> 58\%$ . Results obtained prior the screening period are acceptable provided no potentially cardiotoxic medication was administered between that evaluation and the first dose of decitabine (Cycle 1 Day 1).

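### A routine marrow up to 28 days old can serve for screening with no condition on antileukemic treatment given after it, so a remission from earlier treatment could be scored as a study CR/CRi

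*Combined protocol and SAP*

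**What the plan says.** Section 4 sets the screening window: "Screening for eligible subjects will be performed within 14 days before administration of any study drug". Section 9.1.2 then widens it for routine results, among them "bone marrow collection for morphology, cytogenetics, and either immunohistochemistry or immunofluorescence performed up to 28 days before Cycle 1 Day 1". No condition on later treatment is attached to the marrow.

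Cardiac results are handled differently in the same paragraph: "Results obtained prior the screening period are acceptable provided no potentially cardiotoxic therapy was provided between that evaluation and the first dose of decitabine". Inclusion criterion 6 and footnote j of the Time and Events Schedule repeat that condition.

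The marrow blast count decides eligibility under inclusion criterion 3.1: "Subjects in relapse must have at least 5% blasts in the bone marrow", and "Subjects refractory to previous chemotherapy must have at least 20% blasts in the bone marrow". Neither threshold says when the marrow must have been taken relative to the last treatment.

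On earlier treatment, inclusion criterion 5 says "Subject must be recovered from acute toxicity of any prior treatment". The only stated interval, more than 3 months, applies to transplant. Section 8 adds "Prophylactic intrathecal therapy and hydroxyurea are allowed until 1 day prior to Cycle 1 Day 1" and is silent on systemic chemotherapy before Day 1.

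For the Phase 2 primary endpoint, Section 9.2.1 asks for no minimum duration of CR or CRi. Section 11.4 takes the best response seen over the first four cycles.

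**The concern.** Phase 2 has a single arm, so a CR or CRi is attributed to the study regimen simply because it is observed on study. That attribution needs evidence that leukemia was present when the regimen started. A marrow taken before an intervening course of treatment does not supply it. Such a child can meet the blast threshold on the old marrow, start Cycle 1 with the marrow already clearing, and be counted as a responder at the end of Cycle 1.

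Section 11.4 says the response analysis is meant to help decide on further development, and it judges the count of responders against 20% and 35% in 15 subjects. With so few subjects, one misattributed response changes the picture visibly. The plan already contains the kind of condition that is needed, but applies it to the cardiac tests and not to the marrow.

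**Working it through.** **Step 1: does any other text make the marrow post-date the last treatment?**

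| Provision | What it does | What it leaves open |
|---|---|---|
| Note at the end of Section 4.2 | Excludes subjects who stop meeting the criteria between screening and first dose | Requires no repeat marrow, so clearing can go unseen; does not reach back to Day -28 |
| Exclusion 8.1 | Bars subjects in the treatment phase of another interventional study | Treatment outside a study |
| Exclusion 11 | Lets the investigator exclude for conditions that would interfere with assessments | Discretionary |
| Section 8, ban on other anticancer chemotherapy | Applies during the study | Start point not defined; cannot cover treatment before consent |
| Footnote e | Collects dates of prior treatments | No analysis rule in Section 11 uses them |

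None of them does.

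**Step 2: reproduce the plan's figures.** Inputs from Section 11.4 and Table 5: N = 15, uninteresting rate 20%, interesting rate 35%. The false-positive error for x responders is P(X ≥ x), with X binomial (15, 0.20). This gives 35.2%, 16.4%, 6.1% and 1.8% for x = 4, 5, 6 and 7, as printed. All seven rows of Table 5, including the exact intervals and false-negative errors, reproduce to one decimal.

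**Step 3: add carried-over responders.** Assumption: k of the 15 would be scored CR/CRi because of earlier treatment, and the other 15 − k respond at a true 20%.

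- Expected observed rate = [k + 0.20 × (15 − k)] / 15.
- P(at least x responders) = P(Y ≥ x − k), with Y binomial (15 − k, 0.20).

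| k (assumed) | Expected observed rate | P(≥5 of 15) | P(≥6 of 15) |
|---|---|---|---|
| 0 | 3.0/15 = 20.0% | 16.4% | 6.1% |
| 1 | 3.8/15 = 25.3% | 30.2% | 13.0% |
| 2 | 4.6/15 = 30.7% | 49.8% | 25.3% |
| 3 | 5.4/15 = 36.0% | 72.5% | 44.2% |

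Each carried-over responder adds a net 0.8 responders (1 − 0.20), or 5.3 percentage points, because one in five would have responded anyway.

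**Step 4: how much carry-over bridges the two benchmarks?** With a carried-over share c, the apparent rate is 0.20 + 0.80c. Setting this to 0.35 gives c = 0.15/0.80 = 18.75%, or 2.8 of 15 subjects.

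**The case against.** The best defence is that the case is narrow. Inclusion criterion 3.1 requires relapsed or refractory AML with no curative therapy, and a child just reinduced, with the outcome not yet assessed, does not plainly meet it. Criterion 5 requires recovery from acute toxicity, and a full reinduction plus recovery must fit within 28 days. The plan itself allows up to 42 days for marrow recovery after its own Cycle 1 (Section 3.1.1). The provisions in Step 1 narrow the case further, and accepting a routine marrow spares a child a second aspirate. All of this stands and bears on frequency. It does not supply the missing rule, because recovery is not defined and the old marrow can itself be the evidence of relapse.

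A reader might infer more than the documents support:

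- **That the primary endpoint is a before/after comparison, so any old marrow distorts it.** CR and CRi use an absolute criterion of under 5% blasts (Section 9.2.1). Only PR and marrow progression use the pretreatment value. An old marrow alone does not create a CR; effective treatment given after it can.
- **That disease growth after an old marrow would turn true responses into progression.** Section 9.2.1 does not say whether its rise of more than 25% is relative or in percentage points. The change proposed here would not address growth in any case.
- **That recent chemotherapy would inflate the DLT count.** Section 9.2.2 requires relatedness for Grade 3 or higher non-hematological events and exclusion of other causes of the cytopenia. A condition on the marrow would not change this.
- **That the second-remission rates of 50% to 90% in Section 1.1.1 measure the carry-over.** Those rates are by length of first remission, whereas this trial also admits refractory and post-transplant children. Section 1.2 gives 17% to 69% for cytarabine combinations in pediatric AML. Neither range says how many subjects would be treated between the marrow and Day 1.

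**Conclusion.** The gap in the text is certain; its effect on the result is not. The plan permits a marrow up to 28 days old with no condition on later antileukemic treatment, and the partial safeguards do not close this. A remission from earlier treatment could therefore be scored as a study CR/CRi.

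The size rests on an assumed number of carried-over responders, from 0 to a few of 15, since the documents give no frequency and zero is possible. At a true rate of 20%, the table in Step 3 shows the chance of 6 or more responders roughly doubling with one such subject and roughly quadrupling with two. The correction is worth making because it is cheap and protects attribution of the primary endpoint. There is no evidence that the endpoint is in fact compromised.

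**What to change.** In Section 9.1.2 and in footnote k of the Time and Events Schedule, add: any marrow used for eligibility and as the response baseline, whether from Day -28 to -15 or from Day -14 to 0, is acceptable only if no antileukemic treatment other than the already permitted hydroxyurea or prophylactic intrathecal therapy was given between that marrow and Cycle 1 Day 1; otherwise the screening aspirate is done after that treatment. Both windows must be named, because a condition on the older marrows alone would miss treatment given after a Day -14 marrow.

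For subjects already enrolled, add a sensitivity analysis of CR + CRi. Use the prior-treatment dates collected under footnote e and the date of the baseline marrow. Keep in the denominator any subject treated between that marrow and Day 1, and count that subject as a non-responder. This is deliberately conservative, since some of these subjects would have responded to the study regimen.

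The cost is one sentence in an amendment, one extra table, and an occasional repeat aspirate, which is a real burden for the child concerned. The schedule already lists an aspirate at Day -14 to 0. No washout length is proposed; whether to set one is a clinical decision.

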### 9.1.3. Sequential Treatment Phase

Subjects are to receive sequential treatment in either the Phase 1 or Phase 2 portion of the study. Details of the procedures performed during the Treatment Phase are specified in the Time and Events Schedule. The Sequential Treatment Phase (DACOGEN – cytarabine) begins on Cycle 1 Day 1 and continues until the completion of 4 cycles of treatment, provided there is no evidence of disease progression, unacceptable toxicity, or for the other reasons outlined in Section 10.2.

Subjects will be closely monitored for adverse events, laboratory abnormalities, and clinical response. Clinical evaluations and laboratory studies may be repeated more frequently, if clinically indicated. The next cycle can be started per investigator decision as long as the subject has recovered from acute toxicity and does not meet any of the discontinuation

criteria (Section 10.2). If disease progression is diagnosed, then the subject will discontinue the study treatment, complete the End of Sequential Treatment Visit, End of Treatment Visit, and enter the Follow-up Phase.

#### **9.1.4. End of Sequential Treatment Visit**

Subjects will be treated for a maximum of 4 cycles with DACOGEN - cytarabine sequential therapy. Once a patient completes or discontinues the sequential treatment portion of the study they will have the End of Sequential Treatment Visit at the end of the last cycle of sequential therapy.

#### **9.1.5. Continuation Phase**

After completing up to 4 cycles of sequential DACOGEN - cytarabine treatment or discontinuing sequential treatment for reasons other than progressive disease, subjects who, in the opinion of the treating physician are deriving benefit from DACOGEN treatment can continue to receive single agent DACOGEN at 20 mg/m^2 IV infusion over 1 hour on Days 1-5 every 28 days in the study continuation phase for as long as such treatment is considered beneficial. Treatment may continue at the investigators discretion until the patient is either eligible for transplant, has progressive disease, or experiences unacceptable toxicity.

Subjects who start single agent DACOGEN will be followed for safety and efficacy until the treatment ends. In the event subjects continue to derive benefit at study end, DACOGEN will continue to be supplied by the Company.

